All patients will be admitted after surgery. It is anticipated that some subjects may opt to not continue with VR and withdraw from the study. Participants will be told that they may withdraw from the study at any time by reaching out to the PI, [name], or the study coordinator, [name]. Withdrawing from the study will not affect patient care. A patient may also decline participation for a VR session, but choose not to withdraw from the entire study. If a patient declines three consecutive VR sessions, then they will be withdrawn from the study. If a patient withdraws, any data already collected will be made de-identifiable and no further information will be collected. These patients will not be included in downstream analyses.

Retrospective Cohort:

These patients will not be approached for consent and therefore will not be able to withdraw from the study.

Study Procedures

Due to the limited number of corrective surgeries for scoliosis in a given year, a true randomized control trial cannot be performed. As such, a prospective cohort will be used – all patients undergoing surgery during the study period will be offered VR and will be assessed for pain, opioid usage, and mobilization following surgery. These outcome measures will be compared to data identified from a retrospective chart review of children receiving the same surgery but without an additional VR-intervention, thus serving as a historical control.

Prospective Arm:

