
Retrospective Arm:

Eligible patients verified for the retrospective chart review will be entered into a secure Excel enrollment log and be deidentified by using a subject identification number. The MRN and subject ID will be entered into a linking file that will be password protected and only accessible to authorized study personnel. The following information will be collected from the patient charts: demographics, degree of scoliosis, surgical details, PT notes, pain medication regimens, associated pain scales, and relevant follow up notes. These data will be entered into REDCap in a de-identified manner and will only be accessible to authorized study team members.

Sample Size Justification

This study will utilize a convenience sample of patients presenting to Connecticut Children's for a scoliosis surgery within the study timeframe.

Feasibility, Accrual, and Duration of Accrual

Accrual will occur over a 12 month period (03/01/24 - 03/01/25). Approximately 60-80 patients undergo a surgical procedure for the correction of scoliosis annually at Connecticut Children's. We estimate ~40% will decline to participate, therefore we anticipate approximately 35-50 patients being included in the prospective arm of study. For the retrospective arm of the study, we approximate to include 350 patients for chart review.

Study Limitations

This study is limited in that we are only assessing the utility of VR to reduce pain in a specific patient population (pediatric patients undergoing surgical correction of scoliosis), at a specific time (the immediate post-operative period), at a single institution (Connecticut Children's), and within a relatively small sample size, which limits the generalizability of the study to apply to other patient populations. This study is also limited in that it utilizes a retrospective chart review as a historical control. By collecting data retrospectively, it is likely that the study team will encounter missing variables and will not be able to categorize pain as accurately as they would be able to in a prospective or true randomized control trial study designs.

Data Analysis

- Intention to treat analysis
- A biostatistician will assist in analysis
- Descriptive statistics (frequency, percentage, mean, standard deviation, median, and interquartile range) will be utilized to describe the two groups (VR and control)

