- Fisher's Exact test, independent t-tests, and Wilcoxon Rank Sum tests will be used for univariate analysis to compare demographics between the two groups (VR and control)
- Pain outcome:
 - Univariate analysis using independent t-tests or Wilcoxon rank sum tests will be used to compare the daily mean pain scales
- Opioid utilization outcome
 - Univariate analysis using independent t-tests or Wilcoxon rank sum tests will be used to compare the total inpatient dose of opioids administered

Administrative Organization/Roles and Responsibilities

- Principal Investigator - [name] - Connecticut Children's Division of Neurosurgery
- Co-Principal Investigator – [name] – UConn Department of Psychological Sciences
- Co-Principal Investigator – [name] – Connecticut Children's Division of Orthopedic Surgery
- Co-Principal Investigator – [name] MPH – Connecticut Children's Division of Pain and Palliative Medicine
- Student Coordinators and Responsibilities:
 - [name] – Study Coordinator
 - Study Design

- Data quality
- Data analysis
- Project management
- Manuscript drafting
- [name] – Medical student
 - Study design
 - Study Procedures
 - Data analysis
 - Manuscript drafting
- [name] – Medical Student
 - Study Design
 - Study procedures
 - Data analysis
 - Manuscript drafting

Use of Study Results

The data generated from this study will be used to re-evaluate the postoperative pain management pathway for pediatric patients in the post-operative period following spinal deformity surgery. These data will also be used for presentations / publications.

Study Budget

Item	Quantity	Per
VR Computer	1	\$3,100
VIVE Wireless Head Mounted Display	1	\$1,100
Cleanbox	1	\$2,000
Computer supplies (external hard drives, batteries, sanitizer wipes)	1	\$200
VR Software	1	\$500
TOTAL		\$6,900

References:

1. Janicki, J.A. and B. Alman, *Scoliosis: Review of diagnosis and treatment*. Paediatr Child Health, 2007. **12**(9): p. 771-6.

2. Al-Mohrej, O.A., S.S. Aldakhil, M.A. Al-Rabiah, and A.M. Al-Rabiah, *Surgical treatment of adolescent idiopathic scoliosis: Complications*. Ann Med Surg (Lond), 2020. **52**: p. 19-23.
3. Sung, S., et al., *Incidence and Surgery Rate of Idiopathic Scoliosis: A Nationwide Database Study*. Int J Environ Res Public Health, 2021. **18**(15).

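### The plan claims intention to treat but removes withdrawn VR patients, including those withdrawn for declining sessions, while no such filter applies to the historical controls

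*Combined protocol and SAP*

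**What the plan says.** Data Analysis lists "Intention to treat analysis" as its first item, with no modified definition. For pain, t-tests or rank sum tests "will be used to compare the daily mean pain scales".

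Study Retention/Withdrawal, Prospective Cohort, expects losses: "It is anticipated that some subjects may opt to not continue with VR and withdraw from the study". It lets patients skip sessions and stay in: "A patient may also decline participation for a VR session, but choose not to withdraw from the entire study". It then sets a limit: "If a patient declines three consecutive VR sessions, then they will be withdrawn from the study". After withdrawal, "any data already collected will be made de-identifiable and no further information will be collected", and finally: "These patients will not be included in downstream analyses".

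The Retrospective Cohort paragraph of the same section states that control patients cannot withdraw. Under Study Procedures, Prospective Arm, VR is given twice a day from postoperative day 1, and PT session counts and opioid totals are taken from the chart after discharge. A session with more than half the time off the device is called failed, but no rule withdraws the patient for it.

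**The concern.** Intention to treat, in a study without randomisation, can only mean that every patient enrolled to receive VR is analysed in the VR group. The withdrawal section forbids that. Two analysts following this document could build different primary datasets, and the findings "will be used to re-evaluate the postoperative pain management pathway".

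The exclusion is one-sided. It acts on an arm of 35-50 patients and not on about 350 controls, and the outcome comparisons are univariate, so nothing in the analysis would offset it. If the removed patients have more pain than the rest, the comparison leans toward VR; if less, against it.

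It also discards obtainable data. Opioid and PT totals stay in the chart, yet a withdrawn patient loses both. Patients who stop because of side effects drop out of the side-effect outcome, where they matter most.

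**Working it through.** **Sections side by side.** Data Analysis: all enrolled VR patients, by the ordinary meaning of the term. Study Retention/Withdrawal: enrolled VR patients minus those who withdraw and, on the natural reading, minus those withdrawn after three consecutive declines. Patients with fewer consecutive declines, or with failed sessions, stay in. The set is therefore only partly filtered on adherence: it is neither intention to treat nor strictly per-protocol. Study Limitations does not mention the point, and no sensitivity analysis is planned.

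**Timing.** With two sessions a day from day 1, the third consecutive decline can come no earlier than the first session of day 2. Day 1 scores may exist for these patients and would be dropped too.

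**Arm sizes (Feasibility section).** 60 × 0.6 = 36 and 80 × 0.6 = 48, which agrees with the stated 35-50. Five years at 60-80 a year gives 300-400, midpoint 350, as stated.

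**Effect of the exclusion.** The following are assumptions, not in the documents: 42 enrolled (midpoint of 36 and 48), SD 2, two-sided 5% test, groups otherwise comparable, no true VR effect. Let p be the share removed and d the mean pain of removed minus retained patients, both for one daily comparison.

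- Fall in the VR mean = p × d
- SE = 2 × √(1/[42(1 − p)] + 1/350)
- P(false result favouring VR) = P(Z > 1.96 − p·d/SE)

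For p = 0.20: SE = 2 × √(1/33.6 + 1/350) = 0.361. For p = 0.10: SE = 2 × √(1/37.8 + 1/350) = 0.342.

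| p | d | Shift (points) | False result favouring VR | Range: 35-50 enrolled, SD 1.5-2.5 |
|---|---|---|---|---|
| any | 0 | 0 | 2.5% | 2.5% |
| 10% | 1 | 0.10 toward VR | 4.8% | 4.0-6.2% |
| 20% | 1.5 | 0.30 toward VR | 12.9% | 8.9-22.3% |
| 20% | 2 | 0.40 toward VR | 19.7% | 12.6-35.9% |
| 20% | −1 | 0.20 against VR | 0.6% | 0.3-0.9% |

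In the last row the chance of a false result against VR is P(Z < −1.96 + 0.20/0.361) = 8.0% (6.0-12.3%).

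**Check with whole patients.** Removing 8 of 42 with d = 2 gives a shift of 0.381, SE 0.359 and 18.4% by the formula. Simulation gives 18.8% for the t-test (20,000 runs) and 17.8% for the rank sum test (6,000 runs). At d = 0 both give 2.4%.

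**Several days.** If three days were each tested without correction (between-day correlation 0.5-0.8, assumed), the chance of at least one false result favouring VR would be 31-38% at p = 20%, d = 2, against 5-6% at d = 0. The documents do not fix the number of days, and the 5-6% is multiplicity alone.

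**Could retained early data settle it?** Baseline pain and other pre-withdrawal data are kept de-identified, so withdrawn and retained patients could be compared. The 95% half-width is t × SD × √(1/k + 1/(n − k)). For 8 against 34 it is 2.021 × 0.786 = 1.6 points (1.1-2.2 over the same range with 20% removed). For 4 against 38 it is 2.021 × 1.051 = 2.1 points. A gap of 1-2 points could easily be missed, and outcomes after withdrawal are not collected at all.

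**The case against.** The withdrawal section is specific and the intention-to-treat entry is a bare bullet. In a non-randomised study there is no allocation to preserve. One can read the two together: patients still in the study count as VR whatever their session uptake, and withdrawn patients are out. On that reading only the label is wrong. Voluntary withdrawal is the patient's choice and not an adherence filter, and stopping collection is an ordinary protection when minors withdraw. Every input to the size calculation is assumed, and the mildest non-zero case moves 2.5% only to 4.8%. Larger selection remains in any case: about 40% decline, a 5-minute screen removes others, and the controls come from earlier years.

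Much of this stands. The filter is partial, the bias is unproven in size and direction, and the fix does not touch the other selection. Data Analysis names no test for PT sessions or side effects, so the loss there is to listed outcomes rather than to a planned test. A patient who reaches the limit at the first session of day 2 has declined both day 1 sessions and may lack session-linked scores.

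The central point is not answered. The conciliatory reading leaves a false label on the primary analysis and keeps the one-sided exclusion. The three-decline rule also removes patients who never revoked permission to use their data.

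**Conclusion.** The concern holds and needs correcting before analysis, and during accrual where possible, because outcomes left uncollected may not be recoverable. The judgement rests on the contradiction over who is in the primary comparison, not on a demonstrated bias. The illustrative shift of 0.40 point is 40% of the 1-point difference in the primary hypothesis. It depends on the assumed 20% removal and 2-point gap, and the corresponding 19.7% also depends on the assumed SD and test level. With no gap between removed and retained patients the shift is zero.

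**What to change.** Reconcile the two sections through the analysis set and data collection only:

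1. Replace the exclusion sentence with a rule that every patient who consented, passed the 5-minute screen and had the eligible surgery is analysed in the VR group regardless of session uptake. Report separately those who consented but did not have the surgery.
2. Treat declined sessions, including three in a row, as recorded non-adherence and not as withdrawal from data collection. Continue collecting chart pain scores, opioid totals, PT sessions and side effects to discharge. State that the between-group pain comparison uses chart scores, which both arms have, because a patient who declines VR may lack session-linked scores.
3. For a patient who withdraws permission for data use, stop collection, use earlier data as far as the consent allows, and count later outcomes as missing.
4. Report numbers declining or withdrawing, with reasons, and compare available pre-withdrawal data with a confidence interval.
5. Label any adherent-only analysis secondary and per-protocol.

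Whether VR continues to be offered after declined sessions is for the sponsor to decide.

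The cost is protocol wording, modest extra chart work and a check of the consent text. The recruitment section says consent covers record access, but the consent pages were not available for this review. The VR estimate will be somewhat diluted by patients who used little VR.

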 - Hypothesis: The mean self-reported pain level using a 10-point numeric pain scale will be a minimum of 1 point lower in patients receiving VR compared to those in the control group.

Secondary Aims:

- To determine if VR reduces the total amount of inpatient narcotic use in the acute post-operative period (until discharge) following spinal deformity surgery.
 - Hypothesis: Patients receiving VR will have reduced total inpatient narcotic administration during their hospital stay compared to those in the control group.
- To determine if VR can facilitate earlier mobilization following spinal deformity surgery.

- Hypothesis: Patients receiving VR will participate in a fewer number of physical therapy (PT) sessions prior to receiving clearance for discharge by PT staff.

Outcome Definitions/Data Points Collected

Primary Outcome:

Pain will be measured through the 10-point numeric pain scale self-reported by the patient (patient's will be between 13-18 years of age).

Secondary Outcomes:

- Mobilization will be assessed by the number of PT sessions prior to receiving clearance for discharge by PT staff.
- Patient post-operative gross motor activity level will be measured via wearable Fitbit
- Opioid utilization will be assessed by calculating the total inpatient dose of opioids administered (as documented in the EMR) during the post-operative period.
- Side effects from virtual therapy, including headaches, vertigo, and nausea

Data collected:

- Patient demographics
 - Age, Sex, Race, Language, Ethnicity
- Patient Past Medical History
- Patient medication/drug history (prescription and recreational)
- Prior experience with VR
- Surgical details
 - # of spinal levels involved in fusion
 - Duration of surgery
 - Surgical blood loss
 - Need for transfusion
 - Complications
- Radiographic imaging
- 10-point numeric pain scale ratingsPhysical Therapy notes
 - Number of sessions prior to discharge clearance, timing of sessions, duration of each session, comments from each session,
- EPIC Medication History
- Length of stay
- Timing and duration of virtual reality sessions
- Side effects from virtual therapy sessions
 - Seizures
 - Loss of awareness
 - Headaches
 - Vertigo
 - Nausea
 - Eye strain / blurred or double vision
 - Eye or muscle twitching

- Involuntary movements
- Dizziness and lightheadedness
- Disorientation
- Impaired balance and hand-eye coordination
- Excessive sweating
- Increased salivation
- Drowsiness
- Fatigue
- Motion sickness

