After consenting to the study, the following baseline assessments will be performed and collected from the patient during the pre-operative stage: pain level and vital signs (heart rate, blood pressure, O2 saturation). Starting on postoperative day 1, the prospective cohort will begin receiving VR. These sessions will occur twice daily, starting 30 minutes prior to the patient's scheduled PT appointments, and will be facilitated by a study team member. At the beginning of the session, a study team member will visit the patient's room and set up the virtual reality device. A study team member will try to stay with the patient for the duration of the VR session, but in the event that they are unavailable to do so, a member of the nursing team, physical therapy team, or a parent will remain with the participant. As such, there will always be an adult in close proximity to the participant while they use the VR device. The duration of the session will last approximately 20 minutes and will utilize a low physical load VR experience (underwater or space exploration). The goal of the VR experience is to immerse the patient in a setting that gives the experience of decreased weight bearing load to decrease their post-operative pain. The VR screen will display a simulated environment, such as an underwater exploration, in which the participant can interact with floating marine life and vegetation. If the patient experiences side effects or would like a break during the VR intervention, they can inform a study team member and remove the VR device. They are permitted to place the VR device back on and continue the session when they feel comfortable to do so. A session will be considered "failed" if more than 50% of the session is spent not using the VR device. During the post-operative stage, the above outcome measures will be reassessed daily immediately before and after VR and also following the PT session. After the patient is discharged, the total number of PT sessions and total administered opioids will be collected from the patient's medical charts. In addition to pain, opioid usage, and mobility data from the study, the following information will be collected from the patient charts and entered into REDCap: demographics, degree of scoliosis, surgical details, PT notes, pain medication regimens, associated pain scales, and relevant follow up notes. As the VR device will be shared between users, the device will be sanitized with UV LEDs by Cleanbox prior to the transfer between patients.

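### Patients who stop VR are dropped from every analysis, including the side-effect outcome, so the reported side-effect rate may be too low

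*Combined protocol and SAP*

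**What the plan says.** The rule is in the combined protocol and SAP, Study Retention/Withdrawal, Prospective Cohort. Dropout is expected: "It is anticipated that some subjects may opt to not continue with VR and withdraw from the study". Refusing single sessions is allowed: "A patient may also decline participation for a VR session, but choose not to withdraw from the entire study". Repeated refusal is not: "If a patient declines three consecutive VR sessions, then they will be withdrawn from the study". For a patient who withdraws, "any data already collected will be made de-identifiable and no further information will be collected", and then: "These patients will not be included in downstream analyses". No outcome is exempted.

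Outcome Definitions/Data Points Collected lists as a secondary outcome: "Side effects from virtual therapy, including headaches, vertigo, and nausea". The data list beneath it adds a longer checklist that includes seizures and loss of awareness.

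Study Procedures, Prospective Arm, says of VR: "These sessions will occur twice daily". A patient with side effects may take the device off, and of such patients it says: "They are permitted to place the VR device back on and continue the session".

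Data Analysis opens with a one-line commitment to intention to treat. It then names tests for demographics, pain and opioid dose. Side effects get only the generic descriptive statistics, with no denominator and no safety population.

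**The concern.** The side-effect outcome is meant to show how well these patients tolerate VR. The exclusion is triggered by stopping VR, and intolerance is one plausible reason for stopping. A patient who has vertigo, refuses the next three sessions and is withdrawn would have that vertigo on file but not in the summary.

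Under Use of Study Results, the findings are to feed into a re-evaluation of the post-operative pain pathway. That decision needs the side-effect rate among everyone who started VR. A rate confined to those who kept going answers a different question and may look more favourable.

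**Working it through.** **The plan's own denominator.** Feasibility, Accrual, and Duration of Accrual gives 60-80 operations a year and about 40% declining. 60 × 0.6 = 36 and 80 × 0.6 = 48, which agrees with the stated 35-50. I use 42, which lies within that range. The plan gives no side-effect rate, no withdrawal rate and no length of stay, so every other input below is assumed.

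**Which patients the exclusion reaches.**
- Patients who pause, or who decline one or two sessions without withdrawing, are not excluded by this rule. A session counted as failed has no stated consequence for analysis.
- Voluntary withdrawal can happen at any time.
- The three-session rule needs three refusals after the side effect. With N scheduled sessions, it can act only on a side effect in sessions 1 to N − 3. At two sessions a day, assumed stays of 2, 3 or 4 days give N = 4, 6 or 8, so it can act on side effects in the first 1, 3 or 5 sessions.

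**Expected reported rate.** Let p be the true proportion affected, w1 the withdrawal probability in affected patients and w0 that in unaffected patients.

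Reported rate = p(1 − w1) / [p(1 − w1) + (1 − p)(1 − w0)]

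With p = 0.20 and w0 = 0.10, the second term of the denominator is 0.80 × 0.90 = 0.72:

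| w1 | Calculation | Reported rate |
|---|---|---|
| 0.05 | 0.19 / 0.91 | 20.9% |
| 0.10 | 0.18 / 0.90 | 20.0% |
| 0.15 | 0.17 / 0.89 | 19.1% |
| 0.25 | 0.15 / 0.87 | 17.2% |
| 0.50 | 0.10 / 0.82 | 12.2% |

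Over p from 0.1 to 0.3, w0 from 0 to 0.10, and w1 from equal to w0 up to 0.50, the ratio of reported to true rate runs from 0.53 (p = 0.1, w1 = 0.5, w0 = 0) to 1.00 (w1 = w0).

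**In counts, with exact (Clopper-Pearson) 95% intervals.** Suppose 42 patients start VR, 8 have a side effect, and 2 unaffected patients withdraw:

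| Affected patients who withdraw | Reported | 95% CI |
|---|---|---|
| None excluded (all 42 kept) | 8/42 = 19.0% | 8.6%-34.1% |
| 1 | 7/39 = 17.9% | 7.5%-33.5% |
| 2 | 6/38 = 15.8% | 6.0%-31.3% |
| 4 | 4/36 = 11.1% | 3.1%-26.1% |

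The largest shift is 19.0 − 11.1 = 7.9 points. The distance from 19.0% to its own lower limit is 19.0 − 8.6 = 10.4 points, so even this shift lies within sampling error.

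**Rare event.** If one patient in 42 is affected and stops, 1/42 (2.4%, upper limit 12.6%) becomes 0/41 (0%, upper limit 8.6%). An event that was observed is reported as not having occurred.

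**The case against.** **Intention to treat already covers this.** Under that principle, patients who refuse three sessions would stay in, and the bias would not arise. The documents strictly establish a contradiction between two sections, and taking the exclusion as governing is an inference. It is a reasonable one: the exclusion is explicit and specific, whereas the intention-to-treat line defines no population. Either way the text needs correcting.

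**The problem is broader.** The same exclusion affects pain, opioid dose and PT sessions, and side effects have no stated analysis at all. Both points are true. They add to the case for amending the section, and neither removes this consequence.

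**Materiality is not shown.** All rates are assumed. The 4/36 case needs 4 of 8 affected patients to withdraw against 2 of 34 unaffected. The 5-minute pre-operative screen (Sampling Method/Recruitment Process), the permitted breaks and the freedom to refuse single sessions all make such a gap less likely. In a short stay the three-session rule has little room to act. This stands as a limit on the likely size. But the screen is shorter than the roughly 20-minute post-operative sessions and cannot rule out later intolerance. A confidence interval conveys sampling error; it does not reveal that recorded events were left out.

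**The exclusion may be a promise to participants.** It may reflect a commitment not to analyse withdrawn patients' data. The consent form is not available here, so this cannot be checked, and the fix is made conditional on it.

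**Conclusion.** The concern holds. As written, recorded side effects in patients who withdraw or are withdrawn are left out of the analysis of a secondary outcome that measures them. The data are kept in de-identified form, so the fault is exclusion from analysis and not loss of data.

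The downward direction depends on affected patients stopping more often than unaffected ones, which is plausible but not documented. Equal withdrawal gives no bias, and a reverse gap raises the rate slightly. For common events and modest gaps the effect is small beside the sampling error of 35-50 patients. It matters most for an uncommon event, where one exclusion can turn an observed case into a reported zero. The change should be made. Confidence is medium, because the reading of the rule is well supported but the size is unknown.

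**What to change.** 1. In Study Retention/Withdrawal, directly after the exclusion sentence, add:

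> *Side effects are the exception: those recorded up to withdrawal are included in the side-effect summary, as the consent allows.*

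2. In Data Analysis, add:

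> *Each side effect is reported as the number and proportion of all patients who started at least one post-operative VR session, including those later withdrawn, using data collected up to withdrawal, with an exact 95% confidence interval. The number of sessions started, and the number of patients withdrawn with the reason if given, are reported alongside.*

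This summary describes the VR group only. The reason should be recorded at the time of withdrawal, because the plan stops collecting information afterwards.

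**Cost.** Two short text additions and one data field. There are no new assessments, no follow-up after withdrawal, and no change to the population for pain, opioid or PT outcomes. Whether to keep patients who refuse three sessions in those analyses, and so resolve the conflict with intention to treat there, is a separate decision.

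**Downsides.** The consent must permit use of data collected before withdrawal. Patients who stop early also have fewer sessions at risk, so a per-patient proportion can still understate the risk under full use. Reporting the number of sessions started makes that visible.

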All pediatric patients (ages 13-18) undergoing corrective scoliosis surgery at Connecticut Children's over a span of 12 months (03/01/24-03/01/25) will be approached by a study team member during the pre-operative stage with information and consent documentation about the study. If the patient acknowledges that they are interested and would like more information, then the study team member will complete the formal consent and HIPAA process with the patient and family. This will take place in a private setting, and the patient/family will be given ample time to read the consent and have any questions answered. As a part of the consent and HIPAA, patients will consent to the study procedures as well as the research study team accessing their medical record for data collection. Each patient's MRN will be entered into a secure password protected Excel enrollment log and be given a subject identification number for de-identification. During the consenting procedure, the patient will utilize the VR device for 5 minutes to screen for side effects and become accommodated to the device. In the event that the patient experiences side effects during this 5-minute period, they will be excluded from the study.

Retrospective chart review sample:

The retrospective chart review is intended to be used as a historical control to the prospective arm of the study. All patients in the retrospective time frame (02/01/19 - 02/01/24) will be identified using CPT codes (fusion codes: 22800, 22802, 22804 and instrumentation codes: 22842, 22843, 22844) as well as ICD-10 Code M41.* from Slicer Dicer. These patient's charts will be verified by a study team member to ensure they meet inclusion criteria, and then they will be entered into a using a secure password protected Excel enrollment log. Each patient's MRN will be recorded into the enrollment log and will be given a subject identification number for de-identification. Patients in this cohort will not be approached for consent as we will not collect identifiable information and only their deidentified medical record will be in review. It is also likely that some patients are no longer clinically active at Connecticut Children's, and therefore we would not be able to contact these patients for consent.

Study Retention/Withdrawal

Prospective Cohort:

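### A pre-operative pain baseline is scheduled only in the VR arm and the pain and opioid tests are unadjusted, so a pre-existing pain difference from the historical controls can be neither checked nor removed

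*Combined protocol and SAP*

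**What the plan says.** **VR arm.** Study Procedures, Prospective Arm, schedules a study-collected baseline: "After consenting to the study, the following baseline assessments will be performed and collected from the patient during the pre-operative stage: pain level", together with heart rate, blood pressure and oxygen saturation. Treatment comes later: "Starting on postoperative day 1, the prospective cohort will begin receiving VR". After surgery, "the above outcome measures will be reassessed daily immediately before and after VR and also following the PT session".

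**Controls.** Study Procedures, Retrospective Arm, relies on the chart alone: "The following information will be collected from the patient charts: demographics, degree of scoliosis, surgical details, PT notes, pain medication regimens, associated pain scales", followed by relevant follow-up notes. No time point is attached to the pain scales, and vital signs are not listed. The study-wide list under Outcome Definitions/Data Points Collected includes numeric pain ratings, also without a time point.

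**Analysis.** Data Analysis compares demographics between the two groups, then compares daily mean pain and total inpatient opioid dose by independent t-tests or Wilcoxon rank sum tests. It names no covariate and no change from baseline, and gives the pre-operative pain value no use.

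**VR screen.** Sampling Method/Recruitment Process adds, for the prospective cohort: "During the consenting procedure, the patient will utilize the VR device for 5 minutes to screen for side effects".

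**The concern.** The comparison is non-randomised, against historical controls, and the VR arm passes through filters that the controls do not. About 40% of those approached are expected to decline. Patients with side effects during the VR screen are excluded. Patients who withdraw, including those withdrawn after declining three consecutive sessions, are left out of later analyses. Any of these may be related to how much pain a patient has before surgery, or how well they cope with it.

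Pre-operative pain is an obvious candidate predictor of post-operative pain and opioid need. If the arms differ on it, part of an observed difference predates VR. The plan gives no way to see this, because no comparable value is specified for controls, and no way to correct it, because the tests are unadjusted. The results are meant to inform a re-evaluation of the post-operative pain pathway, so it matters whether a difference near the hypothesised 1 point could have been present before treatment.

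**Working it through.** The plan states no figure to reproduce here. The check sets the sections side by side, followed by an illustration of scale.

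**1. What each arm provides before surgery**

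| Item | VR arm | Controls |
|---|---|---|
| Study-collected pre-operative pain | Scheduled | Not possible (chart review) |
| Charted pain scales | Listed, no time point | Listed, no time point |
| Pre-operative vital signs | Scheduled | Not listed |

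The chart list is the same in both arms: "demographics, degree of scoliosis, surgical details, PT notes, pain medication regimens, associated pain scales, and relevant follow up notes". A common chart source is therefore already in the plan. What is missing is an instruction to take a pre-operative score from it, within a stated window.

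**2. What the analysis does with it**

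Only demographics are compared between groups. Pain and opioid dose are compared by two-group tests without covariates. Pre-operative pain enters no analysis.

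**3. Scale of the possible bias (assumed inputs)**

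The documents give neither the between-group gap in pre-operative pain nor the slope of post-operative on pre-operative pain. I assume a gap of 0.5-1.0 point and a slope of 0.3-0.5. To first order,

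bias in the unadjusted difference = gap × slope.

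| Gap (points) | Slope 0.3 | Slope 0.5 |
|---|---|---|
| 0.5 | 0.5 × 0.3 = 0.15 | 0.5 × 0.5 = 0.25 |
| 1.0 | 1.0 × 0.3 = 0.30 | 1.0 × 0.5 = 0.50 |

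Against the hypothesised minimum effect of 1 point, this is 15% to 50%. It overstates the benefit of VR if the VR patients start with less pain, and understates it if they start with more. The figure describes confounding. It would be the same whenever in the pre-operative stage the VR-arm baseline was taken. No matching figure can be given for opioid dose.

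**4. Order of baseline and VR screen**

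The screen falls within the consenting procedure and the baseline comes after consenting. Read in sequence, the baseline follows 5 minutes of VR. No sentence states the order directly, and no interval is given. For scale, "The duration of the session will last approximately 20 minutes", so the screen is 5/20 = 25% of one session, or 5/40 = 12.5% of a day's two sessions, and it takes place before surgery.

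**The case against.** **Control charts may already hold the score.** The chart item is not restricted to post-operative time, and the contents of Appendix A (Data Collection Tool) are not in the text available, so a pre-operative field may exist there. This stands as a limit on wording: the score is unspecified for controls, not shown to be absent. It does not answer the point, because neither a time window nor a use in the analysis is given.

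**The plan partly covers this.** Study Limitations concedes missing variables and less accurate pain categorisation in the retrospective data, and the exclusion of chronic pain needing daily opioids for more than 2 weeks removes some of the highest pre-operative pain. Both are fair. The first is a general caveat without a remedy. The second trims an extreme and does not balance the rest.

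**A stronger reading on timing.** A reader might infer that the VR-arm baseline is contaminated because it is taken after VR exposure, and that this biases the primary result. The documents do not support that. The order is implied but not stated: the baseline could follow signing of the form and still precede the screen. On either order the value precedes surgery and every VR treatment session, so it is a pre-treatment value. Nothing in the documents shows that a 5-minute tolerance screen shifts it. No planned analysis uses it, so reordering the two steps would change no planned comparison.

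**Conclusion.** The point holds as one about a missing common baseline. In the visible text, a pre-operative pain value is scheduled in one arm only, the corresponding chart item for controls has no time point, and the pain and opioid tests are unadjusted. A pre-operative pain difference between self-selected VR patients and historical controls could be neither checked nor removed.

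The 0.15-0.50 point range rests wholly on the assumed gap and slope. It shows that a modest imbalance could matter against a 1-point hypothesis, not that one exists. The order of the baseline and the VR screen is a matter of clarification only.

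**What to change.** 1. **Study Procedures, both arms:** name as a data item the last charted pre-operative numeric pain score, taken from the same chart source (for example, the pre-operative nursing intake) and within the same time window. Keep the study-collected VR-arm value for description of that arm only, since controls have no counterpart.
2. **Data Analysis:** compare this score between groups. Add regression models for daily mean pain and total opioid dose with group and this score as covariates, alongside the unadjusted tests. Report by arm how many patients lack the score.
3. **Clarification in Study Procedures, Prospective Arm:** state that baseline pain and vital signs are recorded before the 5-minute VR screen.

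**Cost.** One further chart field per patient, for roughly 350 controls and 35-50 VR patients, from charts already being abstracted. Fixing the order of two pre-operative steps costs nothing.

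**Downside.** Some controls will have no charted score and will be missing on the covariate. Adjustment for one charted score removes only the part of the imbalance that this score captures; other differences between volunteers and historical controls remain.
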